4.3 Sample Size

Assuming 4% of subjects do not achieve SVR₁₂ and assuming the 5-year event rate of the composite clinical outcome is 20% in the non-SVR₁₂ subjects, with a 75% reduction in SVR₁₂ subjects (Hazard Ratio of 0.25),^{1,2} then based on two-sample log rank test (using EAST 6.0), a sample size of at least 2000 subjects enrolled in TOPAZ-I (planned to enroll 1650 subjects) and TOPAZ II (planned to enroll 600 subjects) provides greater than 80%

power to reject the null hypothesis of no difference between SVR₁₂ and non-SVR₁₂ subjects in the rate of clinical outcome events. Power calculations were based on a dropout rate of up to 20% for the hazard ratio.

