4.4 Planned Analysis

The primary analysis to evaluate the effect of response to treatment on clinical outcomes, will occur at the final analysis after all subjects have completed the study or prematurely discontinued the study. An interim analysis to assess the percentage of subjects achieving SVR₁₂ will occur after all subjects have completed the Post-Treatment Week 12 Visit or prematurely discontinued the study. For both final and interim analyses, data will be locked after performing appropriate data cleaning. Data after the interim analysis will be added to a subsequent version of the database. SAS[®] (SAS Institute, Inc., Cary, NC) for the UNIX operating system will be used for all analyses. All statistical tests and all confidence intervals will be two-sided with an α level of 0.05.

All analyses will be conducted by statisticians and statistical programmers at AbbVie or the designee according to the methodologies specified in this SAP.

There is no intention of shortening the follow-up time of subjects based on efficacy findings from the interim analysis. The intention is to follow all subjects who receive study drug for 260 weeks following treatment. There will be no statistical adjustment employed due to this interim analysis.

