10.3 Primary Efficacy Analysis

The primary efficacy analysis will be conducted among subjects in the ITT population as described in Section 5.1. HCV RNA values and SVR₁₂ will be imputed as described in Section 6.3.

The primary efficacy endpoint is to assess the effect of response to treatment (as assessed by SVR₁₂ status) on clinical outcomes by comparing the time to incidence of the following events between subjects who achieve SVR₁₂ and those who do not.

- All-cause death
- Liver-related death
- Liver decompensation
- Liver transplantation
- Hepatocellular carcinoma
- Composite of any of the above outcomes

For each of the six event types as listed above, a subject's time to event will be defined as the number of days from the first day of study drug to the day the subject experiences an event of interest. All events of interest will be included, regardless of whether the event occurred while the subject was still taking study drug or had previously discontinued study drug. However, events occurred after a subject started another treatment for HCV will be excluded and the subject will be censored at the time of starting the new HCV treatment. If the subject has not experienced an event of interest nor has the subject died (all-cause death), the subject's data will be censored at the date of the subject's last available assessment of clinical outcomes. All-cause death is a censoring event for liver-related death, liver decompensation, liver transplantation and hepatocellular carcinoma. For subjects with no post-baseline assessment, the subject's data will be censored on the first day of study drug. Time to the composite of clinical outcomes is the time to the first occurrence of any clinical outcome.

For each of the six event types, the distribution of time to event will be estimated for subjects who have achieved SVR₁₂ and those who haven't using Kaplan-Meier methodology and compared between the subjects who have achieved SVR₁₂ and those who haven't using the log-rank test.

For each of the six event types, the 1-, 2-, 3-, 4-, and 5-year event-free survival rate will be estimated using Kaplan-Meier methodology and a 95% confidence interval will be constructed separately for those who have achieved SVR₁₂ and those who haven't.

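### For an event type with only two to four events in total, the log-rank test in SAP 10.3 declares a single non-SVR12 event significant, and the plan has no safeguard for such small counts

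*SAP*

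**What the plan says.** SAP 10.3 lists six event types: all-cause death, liver-related death, decompensation, liver transplantation, hepatocellular carcinoma (HCC) and the composite. For each, the time-to-event distribution is estimated "using Kaplan-Meier methodology and compared between the subjects who have achieved" SVR12 and those who have not, with the log-rank test. A Year-5 Kaplan-Meier test and a Cox model follow for the same six. SAP 4.4 states: "All statistical tests and all confidence intervals will be two-sided with an α level of 0.05". SAP 10.2 makes no multiplicity adjustment.

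The group sizes come from SAP 4.3: "Assuming 4% of subjects do not achieve" SVR12. Power is given for the composite only. Section 10.3 names no exact or permutation version of the test, no minimum event count and no rule for reporting sparse event types descriptively. SAP 10.5 does set such a minimum elsewhere, requiring at least 10 subjects for a subgroup confidence interval.

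**The concern.** The log-rank p-value relies on a normal (chi-square) approximation that needs a reasonable expected number of events in the smaller group. With 4% of the risk set in that group, each event contributes only 0.04 to its expected count. When an event type has very few events, one non-SVR12 event is a large standardised deviation even though it is not an improbable outcome.

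The error also runs in one direction. With so few expected events, observing none in the non-SVR12 group can never be significant, so every false rejection reads as a benefit of SVR12. A p-value of 0.0009 for liver transplantation resting on one subject could then be reported as strong evidence.

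**Working it through.** **Inputs.** Two-sided α 0.05 (SAP 4.4). From SAP 4.3: a 4% non-SVR12 share; a 5-year "event rate of the composite clinical outcome is 20"% in non-SVR12 subjects; "Hazard Ratio of 0.25"; "a sample size of at least 2000 subjects enrolled in TOPAZ-I (planned to enroll 1650 subjects") and "TOPAZ II (planned to enroll 600 subjects"); dropout up to 20%. No rate is given for any single component, so the total event count D is varied below.

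**The plan's own figure.** Take N = 2000 (80 non-SVR12, 1920 SVR12), exponential event times and exponential dropout of 20% over 5 years.
- The non-SVR12 hazard and the dropout hazard are both −ln(0.8)/5. Non-SVR12 events: 80 × 0.5 × (1 − 0.64) = 14.4.
- The SVR12 hazard is a quarter of that. SVR12 events: 1920 × 0.2 × (1 − 0.8^1.25) = 93.5.
- The total is about 108. Schoenfeld power: Φ(√(108 × 0.04 × 0.96) × ln 4 − 1.96) ≈ 80.6%, in line with the SAP's statement that the sample "provides greater than 80"% power.

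**Null behaviour given D events.** The non-SVR12 count X is Binomial(D, 0.04) and Z = (X − 0.04D)/√(0.0384D). The test rejects when |Z| > 1.96. For D = 4 and X = 1, Z² = 0.84²/0.1536 = 4.59, so p = 0.032, whereas P(X ≥ 1) = 1 − 0.96⁴ = 15.1%.

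| Total events D | Log-rank p if one is non-SVR12 | Error rate given D |
|---|---|---|
| 1 | 0.000001 | 4.0% |
| 2 | 0.0009 | 7.8% |
| 3 | 0.0095 | 11.5% |
| 4 | 0.032 | 15.1% |
| 5 | 0.068 | 1.5% |
| 9 | 0.28 | 4.8% |
| 14 (two events needed) | not significant | 10.6% |

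Sampling 80 of 2000 without replacement gives the same values to within 0.1 percentage point.

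**Averaged over a Poisson event count.**

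| Mean events | 1 | 2 | 3 | 4 | 6 | 10 | 15 | 20 | 50 |
|---|---|---|---|---|---|---|---|---|---|
| Error rate | 3.9% | 6.7% | 7.8% | 7.5% | 5.7% | 5.6% | 5.5% | 4.9% | 4.1% |

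Simulating the full log-rank test with 20% dropout gives 6.3%, 7.9%, 6.5%, 5.1% and 4.9% for 5-year risks of 0.1%, 0.2%, 0.3%, 0.5% and 1%.

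**Direction.** With X = 0, Z = −0.04√D/√0.0384 = −0.204√D, which passes −1.96 only at D = 93. Below that count every rejection favours SVR12, so the averaged rates above are to be compared with 2.5% in that direction.

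**Sensitivity to the share at risk.** SAP 10.3 censors subjects who start another HCV treatment, which may remove non-SVR12 subjects preferentially.
- At 3%, one event is significant up to D = 6 (conditional error up to 16.7%, averaged peak 9.4%).
- At 2%, up to D = 8 (14.9%, 8.8%).
- At 5%, only up to D = 3 (14.3%, 7.1%).

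**Composite.** At D = 108 the test rejects for X = 0 or X ≥ 9, with an error rate of 4.2%.

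**The case against.** The other side has several good points.

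- **The 8–15% range is conditional.** It requires exactly 2, 3 or 4 events in both groups combined, about 0.1–0.2% of 2000–2250 subjects. From D = 5 a single event is not significant, and at D = 5–9 the test is at or below its nominal level. A reader might infer that rare outcomes in general carry a 15% error rate. They do not: the averaged rate peaks near 8%.
- **D = 1 gives the most striking p-value but no inflation.** The true probability is 4.0%.
- **Not every component is rare.** Protocol 3.0 cites HCC at about 3% per year in cirrhosis, cut by two-thirds with SVR. With the cap of about 400 cirrhotic subjects filled, 400 × 0.03 × 5 × 1/3 = 20 events in this study alone before dropout, where the averaged error is 4.9%. The same section cites 6.7% 5-year mortality with SVR, so all-cause death is not sparse either.
- **The log-rank test is not the only analysis.** Protocol 8.1.2.1 names Cox regression for this comparison, power is set on the composite, and the study is open-label and non-randomised.

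These points limit the scope. They leave unanswered the fact that a log-rank p-value will be produced for every event type, that no companion analysis is described as a small-sample safeguard, and that the error runs in one direction below 93 events.

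**Conclusion.** The concern holds in a limited form. For an event type that ends with 2–4 total events, one non-SVR12 event gives log-rank p between 0.0009 and 0.032 against a true null probability of 7.8–15.1%. Before the count is known, the error rate peaks at about 8%, or about 9% at a 2–3% share at risk. It is about 5–6% at 6–15 expected events and 5% or less from about 20, but falls entirely on the side of SVR12 below 93 events.

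This rests on the SAP's 4% planning share and on an assumption that some component is that sparse. The documents neither support nor exclude that assumption; liver transplantation and possibly liver-related death are the candidates. The documents do not support extending the claim to HCC, all-cause death or the composite. It is worth correcting because the defect lies in a stated method and the correction is cheap.

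**What to change.** Add to SAP 10.3: for any event type with fewer than 5 expected non-SVR12 events under the null, the log-rank p-value is taken from the exact conditional distribution, a sum of Bernoulli draws with probability equal to the non-SVR12 share of the risk set at each event time. Name the two-sided rule, for example probability ordering. Because it uses the actual risk sets, the method allows for censoring that differs between groups. One non-SVR12 event among 2, 3 or 4 then gives p = 0.078, 0.115 or 0.151.

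Report mid-p beside it, but base any statement of significance on the exact p-value. At D = 2 with one non-SVR12 event, mid-p is 0.0016 + 0.0768/2 = 0.040, so mid-p alone would bring the problem back.

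The composite keeps the standard test if its expected count is at least 5. On the planning figures it is 0.04 × 108 = 4.3, so the rule could reach the composite too. At D = 108 the exact test rejects for the same values (X = 0 or X ≥ 9), so nothing is lost there.

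The cost is a few lines of SAP text and a short macro, with no new data. The downside is conservatism at very low counts: an averaged size of about 1–2%. The rule should be fixed before outcome data are examined.

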 Ribavirin: 200 mg tablet

Doses:	ABT-450/r/ABT-267: 150/100/25 mg QD ABT-333: 250 mg BID Ribavirin: weight-based dosing 1000 or 1200 mg divided twice daily or adjusted for renal impairment subjects
Mode of Administration:	Oral
Reference Therapy:	Not applicable
Dose:	Not applicable
Mode of Administration:	Not applicable
Duration of Treatment:	Subjects will receive ABT-450/r/ABT-267 and ABT-333 with or without RBV for 12 or 24 weeks.
Criteria for Evaluation:	
Efficacy: Plasma HCV RNA (IU/mL) will be assessed at each Treatment and Post-Treatment Visit. Clinical outcomes related to death and the liver will be assessed during treatment and post-treatment.
 
Patient Reported Outcomes (PROs): During treatment and post-treatment, fatigue and general health related quality of life will be assessed using the short form 36 version 2 (SF-36v2) and Functional Assessment of Chronic Illness Therapy – Fatigue (FACIT–F) questionnaires.
 
Safety: Safety and tolerability will be assessed by monitoring adverse events, physical examinations, clinical laboratory tests and vital signs.

Statistical Methods:	
Efficacy: Primary efficacy endpoint is the effect of response to treatment (assessed by SVR12) on clinical outcomes, based on subjects in this study and companion study TOPAZ II. The endpoint will be assessed by comparing the incidence of the following events between subjects who achieve SVR12 and those who do not using the Cox regression model:
 
 
• All-cause death
 
• Liver-related death
 
• Liver decompensation
 
• Liver transplantation
 
• Hepatocellular carcinoma
 
• Composite of any of the above outcomes
 
 
Secondary endpoint analyses:
 
 
• The long-term change from baseline in liver stiffness (as assessed by transient elastography [Fibroscan®]), when available, will be assessed by baseline fibrosis stage and sustained virologic response.
 
• The percentage of subjects achieving SVR12 and 2-sided 95% confidence interval will be presented by baseline fibrosis score (F0-F1, F2, F3 and F4).
 

---

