#### **8.1.2.1 Primary Efficacy Endpoint**

The primary efficacy endpoint is to assess the effect of response to treatment on clinical outcomes by comparing the time to incidence of the following events between subjects who achieve SVR12 and those who do not using a Cox regression model:

- All-cause death
- Liver-related death
- Liver decompensation
- Liver transplantation
- Hepatocellular carcinoma
- Composite of any of the above outcomes

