7.1 Demographic and Baseline Characteristics

Demographics include age, weight, height and BMI as continuous variables, and sex, race, ethnicity, age category (< 55 years or ≥ 55 years] and [< 65 or ≥ 65 years]), birth year (< 1945 , 1945 to 1965, > 1965), country, and BMI category (< 30 kg/m² or ≥ 30 kg/m²).

Baseline characteristics will include: HCV genotype 1 subtype (1a, 1b, 1-other), IL28B genotype ([CC, CT, or TT] and [CC or non CC]), prior treatment history (treatment-naïve [IFN-eligible, IFN-ineligible] or IFN-based treatment-experienced [null responder, partial responder, relapser, prior relapse/breakthrough, prior nonresponder, IFN-intolerant and IFN experienced-other]), baseline HCV RNA levels ([continuous (use log₁₀ HCV RNA)])

and [$< 800,000$ IU/mL or $\geq 800,000$ IU/mL]), baseline HOMA-IR (< 3 or ≥ 3 $\text{mU} \times \text{mmol/L}^2$), baseline fibrosis stage (F0 – F1, F2, F3, F4), baseline Child-Pugh score (non-cirrhotic, 5, 6, or > 6), baseline FibroTest score (continuous and [< 0.49 , $0.49 - 0.58$, $0.59 - 0.74$, ≥ 0.75]), baseline albumin (continuous), baseline albumin (< 35 , ≥ 35 g/L), baseline creatinine clearance (continuous; < 30 mL/min, $\geq 30 - 49$ mL/min, $\geq 50 - 89$ mL/min, ≥ 90 mL/min), baseline eGFR by MDRD (continuous; < 30 , $30 - 59$, $60 - 89$, ≥ 90 mL/min/1.73 m²; < 60 or ≥ 60 mL/min/1.73 m²), baseline platelet count (continuous; $< 90 \times 10^9/\text{L}$, $\geq 90 \times 10^9/\text{L}$; $< 50 \times 10^9/\text{L}$, $\geq 50 \times 10^9/\text{L}$; $< 100 \times 10^9/\text{L}$, $\geq 100 \times 10^9/\text{L}$; $< 150 \times 10^9/\text{L}$, $\geq 150 \times 10^9/\text{L}$), baseline alpha fetoprotein (continuous, and < 20 ng/mL, ≥ 20 ng/mL), tobacco (user, ex-user, or non-user) and alcohol (drinker, ex-drinker, or non-drinker) use status, history of diabetes, history of depression or bipolar disorder, history of bleeding disorders, AST to platelet ratio index (APRI) (continuous; ≤ 2.0 or > 2.0), and Fibrosis-4 score (FIB-4) (continuous; ≤ 3.25 , > 3.25).

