10.2 Handling of Multiplicity

No adjustment for multiple comparisons is used in this open-label long-term outcome study.

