For each of the six event types, a test statistic based on Kaplan-Meier estimates of the event-free survival probability at Year 5 and the estimated variance will be constructed to test the null hypothesis that the 5-year event-free survival rates for subjects who have achieved SVR₁₂ and those who haven't are the same.

For each of the six event types, a Cox proportional hazards (PH) model will be constructed to include all the baseline characteristics as described in Section 7.1, SVR₁₂ status, and other variables as appropriate to compare the risk of experiencing a clinical outcome between subjects who have achieved SVR₁₂ and those who haven't.

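### SAP 10.3 puts an unstratified log-rank test and an unadjusted Year-5 test beside the adjusted Cox model for non-randomised SVR12 groups, and does not say which comparison decides

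*SAP*

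**What the plan says.** The protocol names one method for the primary comparison. The Synopsis (Statistical Methods) compares responders with "those who do not using the Cox regression model", and Protocol 8.1.2.1 compares subjects who achieve SVR12 "and those who do not using a Cox regression model". Neither place lists covariates.

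SAP 10.3 sets out three between-group comparisons for each of six event types:

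- Kaplan-Meier curves, "compared between the subjects who have achieved SVR₁₂ and those who haven't using the log-rank test". No strata are named.
- "a test statistic based on Kaplan-Meier estimates of the event-free survival probability at Year 5", with its estimated variance. No covariates are named.
- "a Cox proportional hazards (PH) model will be constructed to include all the baseline characteristics as described in Section 7.1", together with SVR12 status "and other variables as appropriate". SAP 7.1 lists "baseline fibrosis stage (F0 – F1, F2, F3, F4") among those characteristics.

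SAP 10.2 adds: "No adjustment for multiple comparisons is used in this open-label long-term outcome study". No sentence ranks the three methods or says what follows if they disagree. Protocol 8.2 and SAP 4.3 compute power for this comparison with a two-sample log-rank test.

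**The concern.** Protocol 8.3 confirms that nothing is randomised, and response is observed only after treatment starts, so the SVR12 groups can differ at baseline. Protocol 3.0 says that the risk of decompensation and hepatocellular carcinoma is greatest in advanced fibrosis. It also reports SVR12 in cirrhotic subjects (Study M13-099) of 91.8% at 12 weeks and 95.9% at 24 weeks, against 96.2% in non-cirrhotic treatment-naïve subjects (Study M11-646). If F4 subjects are over-represented among non-responders, an unstratified log-rank or crude Year-5 comparison credits SVR12 with a difference that partly reflects baseline cirrhosis.

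The Cox model in the same section adjusts for fibrosis stage. Because it is not named as decisive, an unadjusted p-value could be reported as the primary result. The sample-size sections could even be read as pointing to the log-rank.

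**Working it through.** **1. The plan's own figure.** Inputs from SAP 4.3: N = 2000, 4% non-SVR12 (80 vs 1920 subjects), 20% five-year events in non-SVR12, HR 0.25, 20% dropout. Hazards per year: non-SVR12 −ln(0.8)/5 = 0.0446; SVR12 0.25 × 0.0446 = 0.0112; dropout 0.0446 (exponential).

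- Non-SVR12 events: 80 × 0.5 × (1 − e^(−0.446)) = 14.4.
- SVR12 events: 1920 × 0.2 × (1 − e^(−0.279)) = 93.5.
- Schoenfeld: √(107.9 × 0.04 × 0.96) × ln 4 − 1.96 = 0.86, so power is 80.6%.

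The stated figure of more than 80% is reproduced and is not in dispute. Simulated log-rank power is about 97%, because the formula is conservative at a 4:96 split.

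**2. Non-response by cirrhosis.** Two readings of the protocol's figures:

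- Whole-study rates: F4 100 − 95.9 = 4.1% (M13-099, 24 weeks); non-F4 100 − 96.2 = 3.8% (M11-646). The 4.1% is 7/172, 95% CI 2.0–8.2%.
- Protocol Table 1 under the Table 5 regimens, weighted by the M13-099 history mix (42.1/36.1/8.2/13.7, sum 100.1) and 68.7% GT1a. Applying that mix to this trial is an assumption.
  - GT1a cirrhotic, 24 weeks: (42.1 + 36.1) × 7.1/100.1 = 5.55%.
  - GT1b cirrhotic: 8.2 × 14.3/100.1 = 1.17%. This rests on one failure in seven subjects.
  - F4: 0.687 × 5.55 + 0.313 × 1.17 = 4.2% (3.8% without that one failure).
  - GT1a non-cirrhotic: (42.1 × 4.3 + 36.1 × 4.6 + 13.7 × 6.0)/100.1 = 4.29%. GT1b non-cirrhotic: 42.1 × 1.0/100.1 = 0.42%.
  - Non-F4: 0.687 × 4.29 + 0.313 × 0.42 = 3.1%.

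Longer use of 12 weeks raises the F4 figure. GT1a cirrhotic non-response at 12 weeks is (42.1 × 7.6 + 36.1 × 20.0 + 13.7 × 6.7)/100.1 = 11.33%. F4 is then 0.687 × (5.55 + 11.33)/2 + 0.313 × 1.17 = 6.2% with half at 12 weeks, and 0.687 × 11.33 + 0.313 × 1.17 = 8.2% with all. With 24 weeks for prior null responders only, GT1a is (42.1 × 7.6 + 36.1 × 7.1 + 13.7 × 6.7)/100.1 = 6.67% and F4 is 0.687 × 6.67 + 0.313 × 1.17 = 5.0%.

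**3. How much imbalance that makes.** The F4 share is taken as 400/1650 = 0.242 (the enrolment cap, also applied to TOPAZ-II by assumption). At 4.2% vs 3.1%:

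- F4 share in non-responders: 0.242 × 4.2/(0.242 × 4.2 + 0.758 × 3.1) = 0.302.
- F4 share in responders: 0.242 × 95.8/(0.242 × 95.8 + 0.758 × 96.9) = 0.240.

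With five-year events of 20% (F4) and 3% (non-F4), the hazard ratio by cirrhosis is ln 0.80/ln 0.97 = 7.33. The crude HR with no true effect is (1 + 0.240 × 6.33)/(1 + 0.302 × 6.33) = 0.87. At 4.1% vs 3.8% the shares are 0.257 and 0.242, and the crude HR is 0.96.

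**4. Rejection with no SVR12 effect within stratum.** N = 2250 (1650 + 600), exponential events, 20% dropout, 5 years, |z| > 1.96, 4000 trials per setting. The 9.2% and 28.2% are the protocol's five-year composite rates with and without SVR in advanced fibrosis or cirrhosis; the other event rates are assumed.

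| Non-response, F4 vs non-F4 | Events 9.2/3% | 20/3% | 28.2/2% |
|---|---|---|---|
| 4.1 vs 3.8% | 5% | 5% | 6% |
| 4.2 vs 3.1% | 6% | 8% | 10% |
| 5.0 vs 3.1% (24 weeks for prior nulls only) | 7% | 11% | 16% |
| 6.2 vs 3.1% (half of GT1a F4 at 12 weeks) | 9% | 18% | 28% |
| 8.2 vs 3.1% (all at 12 weeks) | 13% | 31% | 48% |

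These are for the unstratified log-rank; repeat runs agreed within about 2 points (5–10% in the second row). Stratified by F4, the log-rank rejected about 4–6% in every cell. A Cox model with SVR12, F4 and study rejected 3–5%.

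**5. Power after stratifying** (N = 2000, HR 0.25): unstratified 95–98%, stratified 95–97%, three-term Cox 95–97%.

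**The case against.** The strongest reply is that the SAP already contains the right analysis. That stands. A reader might infer that the SAP drops the protocol's Cox regression, and the text refutes this: SAP 10.3 specifies a Cox model for every event type and adds baseline adjustment that the protocol did not list. Nor is the log-rank an SAP departure, since both documents base power on it.

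The second reply is that the effect is small on inputs tied to the current assignment. That also stands. The 18–48% cells need half or all GT1a cirrhotic subjects at 12 weeks together with the higher event rates. The 28.2% rate belongs to patients without SVR, whereas nearly all F4 subjects here should respond. The documents allow 12 weeks for some subjects but do not say how many.

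Third, the Year-5 test's excess should not be laid to confounding. It rejects 7–11% even at 4.1% vs 3.8%, mainly because events are sparse.

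Fourth, the 4–6% for the stratified test holds when SVR12 status is fixed at time zero. SAP 10.3 counts time from first dose and SAP 6.3 imputes missing HCV RNA as failure, so a death before the SVR12 window generally becomes a non-SVR12 event. If 25–50% of early first events were deaths at a constant hazard (assumed), stratified rejection rises to about 22–50%. Protocol Table 2 shows very few deaths on study, so this is probably harsh, but stratification does not cure it.

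Last, the absence of multiplicity adjustment is declared, and the protocol lists the six outcomes on an equal footing. Making the composite alone decisive would be a design choice and is not claimed here.

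**Conclusion.** The point holds as a gap in SAP 10.3. Two tests without baseline adjustment sit in the primary analysis of non-randomised groups, and the adjusted Cox model lacks the status of deciding comparison. Confounding by cirrhosis is possible on the protocol's own evidence, but its size is open: about 5–6% rejection if non-response is nearly equal and about 5–10% at 4.2% vs 3.1%. Larger figures depend on assumed 12-week use. All of these assume an F4 share of 24%, exponential events and the stated event rates. The documents do not support a claim that the primary result will be seriously biased. They support saying that an avoidable source of bias is left in a p-value that could be reported as primary.

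**What to change.** In SAP 10.3:

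1. Stratify the log-rank test by baseline cirrhosis (F0–F3 vs F4), optionally also by study.
2. State that the adjusted Cox model, the method named in the protocol, is the deciding comparison, with the stratified log-rank supportive. Replace the open covariate wording with a short list fixed in advance that includes baseline fibrosis stage. SAP 7.1 holds many overlapping measures (fibrosis stage, FibroTest, APRI, FIB-4, several platelet cut-points), while the plan's assumptions give only about 14 non-SVR12 events at N = 2000.
3. Label the unstratified log-rank and Year-5 tests descriptive.

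The cost is a few sentences; fibrosis stage and study are already recorded. Power falls by 0–2 points in the three-term Cox simulation, which has not been shown for the full SAP 7.1 model. The test on which power was computed becomes stratified and supportive, and the SAP should say so. The change deals with confounding by cirrhosis only. Other confounders, the sparse-event behaviour of the Year-5 test and deaths before the SVR12 window remain.
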